## 11.5 Summary of Efficacy Analyses

| Endpoint   | Analysis  | Populations |
|--|---|-------------|
| The mean number and intensity of relapses
(primary endpoint)                | Student's t-test, ANOVA, generalized linear mixed model | ITT         |
| The reduction of mean number of relapses (primary endpoint)                    | Student's t-test, ANOVA                                 | ITT         |
| The difference of the level of cell damage and inflammation (primary endpoint) | ANCOVA  | ITT         |
| The changes in IOP (secondary endpoint)  | ANCOVA  | ITT         |
| The changes in OCT (secondary endpoint)  | ANCOVA  | ITT         |
| The changes in BCVA (secondary endpoint)                                       | ANCOVA  | ITT         |
| The presence of keratopathy (secondary endpoint)                               | Chi-square test   | JTT         |
| The presence of synechiae (secondary endpoint)                                 | Chi-square test   | ITT         |
| Information collected through the Quick questionnaire (secondary endpoint)     | Chi-square test   | ITT         |

### 12. SAFETY EVALUATION

Safety and tolerability data will be summarized by treatment group.

Clinical evaluations for safety and tolerability assessments will be included monitoring AEs, vital signs, concomitant medications and compliance.

Statistical Analysis Plan Version no. 1.0 – 20/07/2020

Protocol Code NORFLO-ORO-16 EudraCT number NA

## 12.1 Extent of Exposure

The extent of exposure will be estimated on the treatment duration.

### **12.2** Adverse Events

Adverse event will be coded using the last updated version of the Medical Dictionary for Regulatory Activities (MedDRA) dictionary to give a preferred term (PT) and a system/organ class term (SOC) for each. Adverse events will be tabulated by treatment group. Tables will be included the number of patients who experienced at least one AE, of study product-related AEs (defined as definitely, probably, possibly, or unrelated), of serious AEs, and the number of patients withdrawn due to AE, summarized by treatment arm. Comparisons between treatment arms will be performed using chi-square test.

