13.5 Investigator Responsibilities

The Eye Pharma-investigator will promptly review documented adverse events and abnormal test findings to determine (1) if the abnormal test finding should be classified as an adverse event; (2) if there is a reasonable possibility that the adverse event was caused by the investigational product and (3) if the adverse event meets the criteria for a serious adverse event.

If the Eye Pharma-investigator's final determination of causality is "unknown and of questionable relationship to the investigational product" the adverse event will be classified as associated with the use of the investigational product, for reporting purposes.

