13.6 Evaluation of Causality

AE Relationship to Study Product

The relationship of an AE to the study drug should be assessed using the following the guidelines in Table 5.

Relationship to Product	Comment
Definitely	Previously known toxicity of the agent; or an event that follows a reasonable temporal sequence from administration of the product; that follows a known or expected response pattern to the suspected product; that is confirmed by stopping or reducing the dosage of the product; and that is not explained by any other reasonable hypothesis.
Probably	An event that follows a reasonable temporal sequence from administration of the product; that follows a known or expected response pattern to the suspected product; that is confirmed by stopping or reducing the dosage of the product; and that is unlikely to be explained by the known characteristics of the subject's clinical state or by other interventions.
Possibly	An event that follows a reasonable temporal sequence from administration of the product; that follows a known or expected response pattern to that suspected product; but that could readily have been produced by a number of other factors.
Unrelated	An event that can be determined with certainty to have no relationship to the study product.

Table 5 - AE Relationship to Study Product

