14.5 Safety Evaluations

Safety and tolerability data will be summarized by treatment group.

Clinical evaluations for safety and tolerability assessments will include monitoring AEs, vital signs, concomitant medications and compliance.

Adverse event will be coded using the last updated version of the Medical Dictionary for Regulatory Activities (MedDRA) dictionary to give a preferred term (PT) and a system/organ class term (SOC) for each. Adverse events will be tabulated by treatment group. Tables will include the number of patients who experienced at least one AE, of study product-related AEs (defined as definitely, probably, possibly, or unrelated), of serious AEs, and the number of patients withdrawn due to AE, summarized by treatment arm. Comparisons between treatment arms will be performed using chi-square test.

Concomitant medications will be summarized by treatment using descriptive statistics and they will be listed.

Vital signs will be summarized by treatment using descriptive statistics for absolute values and change from baseline.

Compliance to the study treatment will be assessed through the patient diary and checked versus the used and unused study product containers given back by the patients.

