### **4.2** Treatment Administration

Sixty subjects with HLA-B27-associated uveitis were enrolled and they were divided into 2 groups, 30 received the treatment and 30 the placebo, in addition to conventional therapy. In Italy 46 patients were recruited.

Each subject received a single dose of either placebo or NORFLO® ORO two times a day for 1 year. Subjects were assigned to the treatments in a random order. Evaluations were taken at baseline (t0) and during each of the following two visits within the study (t1 6 months, t2 12 months).

Data from screened patients were reviewed to determine the subject eligibility. Subjects who met all inclusion criteria and none of the exclusion criteria were enrolled in the study and randomized to treatment.

The following treatment regimens were applied:

Statistical Analysis Plan Version no. 1.0 – 20/07/2020 Protocol Code NORFLO-ORO-16 EudraCT number NA

- NORFLO® ORO 1.7450 gr
- Placebo 1.7450 gr

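### The definition of product-related adverse events covers the whole causality scale, including unrelated events, so the related-AE row would repeat the any-AE row

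*SAP*

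**What the plan says.** SAP Section 12.2 lists the contents of the AE tables. They include "the number of patients who experienced at least one AE, of study product-related AEs", serious AEs and withdrawals due to AEs, by arm. The product-related group is given as "study product-related AEs (defined as definitely, probably, possibly, or unrelated), of serious AEs". For the test it says: "Comparisons between treatment arms will be performed using chi-square test".

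Protocol Section 14.5 has the same definition: "study product-related AEs (defined as definitely, probably, possibly, or unrelated), of serious AEs, and the number of patients withdrawn due to AE". The Safety Analysis entry of the protocol synopsis repeats it.

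The causality scale is set in Protocol Section 13.6: "The relationship of an AE to the study drug should be assessed using the following the guidelines in Table 5". Table 5 has four levels: definitely, probably, possibly and unrelated. It describes the last as "An event that can be determined with certainty to have no relationship to the study product".

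Protocol Section 13.5 deals with a final causality judgement of unknown and questionable relationship. In that case "the adverse event will be classified as associated with the use of the investigational product, for reporting purposes".

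**The concern.** An event judged with certainty to have no link to the product cannot also be product-related, yet the definition puts it there. Because the listed terms exhaust the scale, the definition excludes nothing. A programmer who follows the SAP would produce a row labelled product-related that holds every adverse event, and a test on that row that says nothing beyond the any-AE test.

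The safety profile is a stated secondary objective (Protocol Section 3.2, SAP Section 3.2), and this row is the only planned AE summary that uses the causality judgement. A reader of the report would take its percentages as the share of patients with suspected product-related events, and they would be no such thing.

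**Working it through.** The documents state no figure for this point, so there is no plan figure to reproduce. The check compares the definition with the scale.

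**Inputs**
- Scale S (Protocol Section 13.6, Table 5): definitely, probably, possibly, unrelated. Four levels.
- Related set R (SAP Section 12.2, Protocol Section 14.5, synopsis): definitely, probably, possibly, unrelated. Four levels.
- Relation to study product is to be recorded on the CRF for AEs (Protocol Section 9.1.6).
- Missing data are not replaced (SAP Section 9.1.4).

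**Step 1: compare the sets.** S minus R is empty, so R = S, 4 of 4 levels. The Section 13.5 rule does not create an excluded class either, since it moves events towards the product.

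**Step 2: carry this into the table.** In each arm, patients with a related AE = patients with at least one AE whose level is in R = patients with at least one AE that has a causality entry. This equals the any-AE count, less any patients whose AEs all lack an entry. If the row counts events instead of patients, it equals all events with an entry.

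**Step 3: carry this into the test.** With the same patient counts and the same arm totals, the two-by-two table is identical. The chi-square statistic and p-value are then those of the any-AE comparison.

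**Step 4: look for a correction elsewhere.** SAP Section 13, on deviations from the protocol analysis, does not mention the definition. SAP Section 14.3 lists two AE tables by title only, with no shell and no entry by causality.

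**Step 5: apply the correction.** R without unrelated is {definitely, probably, possibly}, 3 of 4 levels, and so a proper subset of all AEs.

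**Direction of the error, by illustration only.** The rates below are assumptions and appear in neither document. Let r be the proportion of patients with a truly related AE and u the proportion with an unrelated AE, independent of r and equal in both arms. The row as written then shows 1 − (1 − r)(1 − u), and the between-arm difference is multiplied by (1 − u). With r = 30% on active and 5% on placebo (true difference 25 points):

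| u | Active, as written | Placebo, as written | Difference |
|---|---|---|---|
| 10% | 1 − 0.70 × 0.90 = 37.0% | 1 − 0.95 × 0.90 = 14.5% | 22.5 points |
| 30% | 1 − 0.70 × 0.70 = 51.0% | 1 − 0.95 × 0.70 = 33.5% | 17.5 points |
| 50% | 1 − 0.70 × 0.50 = 65.0% | 1 − 0.95 × 0.50 = 52.5% | 12.5 points |
| 70% | 1 − 0.70 × 0.30 = 79.0% | 1 − 0.95 × 0.30 = 71.5% | 7.5 points |

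The width of this range shows why no single size can be given.

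**The case against.** The strongest reply is that the parenthesis is a list of reporting categories: AEs would be broken down by relationship, in the order of Table 5, and nothing would be duplicated. That is a plausible intention. But the text introduces the list as a definition of product-related AEs, and no table shell shows a breakdown. If a breakdown was meant, the sentence still needs rewording.

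A second reply is that little is lost, and most of it stands. The safety endpoints (Protocol Section 5.3, SAP Section 5.3) are the incidence and type of all AEs, concomitant medication and vital signs. None is defined on related events. In a randomised, double-blind, placebo-controlled trial, the comparison of all AEs is informative about harm without individual causality judgements. The causality data are collected, and two identical rows would be easy to notice.

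A reader might therefore infer too much in three ways:
- That the product's safety profile could not be assessed. The documents do not support this, because the any-AE, serious-AE and withdrawal counts and the MedDRA coding remain valid.
- That a harm signal of a known size would be hidden. No AE rates are given, so no such size can be derived.
- That Protocol Section 13.5 already obliges the table to count every event of unknown or questionable relationship as related. That section requires both conditions together, applies to a final determination for reporting purposes, and does not address tabulation. Table 5 has no unknown level.

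**Conclusion.** The definition is wrong as written. It contradicts the protocol's own causality table, and the SAP carries the contradiction forward from Protocol Section 14.5 and the synopsis. Followed literally, it makes one planned safety row and its test redundant and mislabels that row. The related-AE rate is overstated in any arm where some patients have only unrelated events.

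What is exact is the inclusion of 4 of 4 causality levels. The duplication rests on two assumptions: that the sentence is programmed literally, and that causality entries are essentially complete. The change in reported percentages cannot be computed from the documents, and the illustrative rates above should not be used to grade the problem. The effect is confined to the causality-specific summary. The correction is worth making because the error is clear and the change is small.

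**What to change.** Before the blind is broken, state in SAP Section 12.2 that product-related means definitely, probably or possibly related, and show unrelated events in their own row. Tabulating AEs by each of the four Table 5 levels would serve equally well. State how AEs with a missing causality entry are counted.

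Optionally, say whether events with a final determination of unknown and questionable relationship count as related in the table. Counting them so would be consistent with Protocol Section 13.5, but it is a choice beyond the correction itself.

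Record the change in SAP Section 13. Protocol Section 14 provides for the SAP to carry modifications to the planned analysis, so a SAP revision is enough. Protocol Section 14.5 and the synopsis can be aligned if the protocol is next revised. The cost is a few sentences and a row in a table shell. The causality judgements are already on the CRF, so no new data are needed.

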### 5.3 Safety Endpoints

The safety endpoints include:

- the incidence and typology of adverse events in the NORFLO® ORO treatment group compared to placebo group;
- the use of concomitant medications:
- the changes in vital signs.

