## 8.3 Safety Population

All eligible patients who are randomized into the study and receive at least one dose of the study product will be included in the safety analysis.

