### 11. EFFICACY ANALYSIS

SAS 9.4 for windows (SAS Institute Inc., Cary, NC, USA) will be used for statistical analysis. A level of statistical significance (alpha) of 5% will be used to evaluate statistically significant differences between the two treatment groups, placebo and active treatment. Parametric tests will be used as the first-choice test. When the dependent variables are not normally distributed, also the non-parametric alternative will be used.

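### Adverse events are compared between arms only by a chi-square test, with no risk difference or interval, so at 30 per arm a non-significant result for uncommon events cannot show what excess remains possible

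*SAP*

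**What the plan says.** Evaluating the safety profile is a secondary objective (Protocol 3.2, SAP 3.2). The first safety endpoint is "the incidence and typology of adverse events in the NORFLO® ORO treatment group compared to placebo group" (SAP 5.3).

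SAP 12.2 tabulates by arm "the number of patients who experienced at least one AE", product-related AEs, serious AEs and withdrawals due to AE. It then adds: "Comparisons between treatment arms will be performed using chi-square test". Protocol 14.5 says the same. The bracketed definition of product-related AEs in both places lists the unrelated category among the related ones.

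Vital signs and concomitant medications are summarised descriptively (SAP 12.3). Neither document names a risk difference, ratio, confidence interval, margin or expected AE rate for safety.

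The 5% level appears in Protocol section 14 for comparisons between the arms in general. The SAP repeats it under section 11, which covers efficacy: "A level of statistical significance (alpha) of 5% will be used to evaluate statistically significant differences". SAP section 12 sets no level of its own.

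The safety population is "All eligible patients who are randomized into the study and receive at least one dose of the study product" (SAP 8.3). On size, SAP 4.2 reports that "30 received the treatment and 30 the placebo".

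**The concern.** The trial was sized on relapse counts. A test on AE proportions at the same sample size may be non-significant whether or not the product causes a relevant excess. A p-value alone does not tell the reader which case applies. An interval does, because it states the largest excess that the data still allow.

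Two further points follow from using a chi-square test on crude proportions:

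- The large-sample approximation is weak when few patients have the event. That could apply to serious AEs and AE withdrawals, which bear most on safety.
- Patients given systemic therapy for a relapse leave the study (Protocol 7.1, 10.4). If the product prevents such relapses, its patients are observed for longer and can show more AEs at the same underlying rate.

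**Working it through.** **The plan's own figure.** SAP section 7 gives SD 0.7, difference 0.6, power 80% and alpha 5%. The normal formula gives n per arm = 2(1.96 + 0.84)² × 0.7² / 0.6² ≈ 21.4, so 22. The t-test version gives 22.4, so 23 per arm, or 46, as stated. Allowing for 20% dropout, 46 / 0.8 = 57.5, against 60 recruited. The figure reproduces, but it concerns relapses. No power or detectable difference is given for AEs.

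**Power of the planned test for AEs.** Inputs are 30 per arm (SAP 4.2) and alpha 5%. Sidedness is not stated, so two-sided is assumed, and so is no continuity correction. For each pair of true rates, the binomial probabilities of all 31 × 31 outcomes with Pearson chi-square above 3.841 are summed. The AE rates are assumptions.

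| Placebo vs active | Power | Missed |
|---|---|---|
| 5% vs 10% | 11% | 89% |
| 10% vs 20% | 19% | 81% |
| 20% vs 40% | 39% | 61% |
| 25% vs 50% | 52% | 48% |
| 30% vs 60% | 66% | 34% |
| 40% vs 80% | 90% | 10% |
| 5% vs 15% | 26% | 74% |
| 10% vs 30% | 50% | 50% |
| 15% vs 45% | 74% | 26% |
| 20% vs 60% | 90% | 10% |

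Power passes 50% at a placebo rate of about 24% for a doubling and about 10% for a tripling. With continuity correction these become about 28% and 12%.

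**What an interval would add.** Take 6/30 on active and 3/30 on placebo.
- Chi-square = 60 × (6×27 − 3×24)² / (30 × 30 × 9 × 51) = 1.18, so p = 0.28.
- The difference is 10 points. The Wilson limits are 9.5% to 37.3% for 6/30 and 3.5% to 25.6% for 3/30.
- Newcombe lower limit: 10 − √[(20 − 9.5)² + (25.6 − 10)²] ≈ −9 points.
- Newcombe upper limit: 10 + √[(37.3 − 20)² + (10 − 3.5)²] ≈ +29 points.

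The p-value reads as no difference, yet an excess of up to 29 points remains possible.

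**Small counts.** The expected number of events per arm is 30 times the pooled rate, so it falls below 5 when the pooled rate is under 5/30 = 16.7%. In the example above it is 4.5. For 4/30 against 0/30 it is 2. There the chi-square is 60 × (4×30)² / (30 × 30 × 4 × 56) = 4.29, p = 0.04, while Fisher's exact p is 2 × C(30,4)/C(60,4) = 2 × 27,405/487,635 = 0.11. The two tests fall on opposite sides of 5%.

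**Unequal follow-up.** Assume the same hazard of h = 0.7 AEs per patient-year in both arms, and a fraction w withdrawn at times spread evenly over the year. The proportion with an AE is (1 − w)(1 − e^−h) + w[1 − (1 − e^−h)/h], which here is 0.503(1 − w) + 0.281w.
- w = 20% active, 50% placebo: 46% vs 39% with an AE; the test rejects about 8% of the time.
- w = 10% vs 30%: rejects 6.5%.
- w = 15% vs 25%: rejects 5.5%.
- Equal withdrawal at 20%: rejects 5.1%.

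The last three average the planned 20% dropout. All withdrawal splits are assumptions.

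**The case against.** A small trial with exploratory aims is not expected to have power for AEs. The documents tabulate counts by arm, code events by term and plan a display of events (SAP Table 14.3.2), so anyone could compute an interval later. That stands, and it is why the point is modest. It does not explain why the plan prints a p-value and no estimate.

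A reader might infer four stronger things, none of which the documents support.

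- **That the test misses any doubling or tripling at least half the time.** This depends on a placebo rate that the documents do not give. If about 40% of placebo patients have some AE over 12 months, a doubling is missed only about 10% of the time.
- **That the plan treats a non-significant result as proof of safety.** Neither document says so. This is a caution about interpretation.
- **That dropout cuts the comparison to 24 per arm.** The safety population keeps every eligible randomised patient with at least one dose.
- **That unequal follow-up seriously distorts the comparison.** On the assumed splits the effect is small. Protocol 11.1 also encourages patients who stop treatment to complete the remaining visits, although 7.1 and 10.4 remove those given systemic therapy from the study. Those passages must be reconciled, because they determine how long AEs are observed.

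**Conclusion.** The concern holds as a limit on what the planned output can show. Chi-square is the only inferential between-arm comparison of AEs, and no effect estimate or interval accompanies it. At 30 per arm, power is below 50% for a doubling when the placebo rate is under about 24%, and for a tripling when it is under about 10%. Above those rates the test does better. That serious AEs and AE withdrawals will be uncommon is an assumption. If they are, a non-significant result says little and the chi-square approximation is unreliable.

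The follow-up bias is secondary: rejection of about 5.5% to 8% at equal hazards, depending on assumed withdrawal. The text contains no false statement about safety, so this is a worthwhile low-cost improvement and not a correction of an error. The listing of unrelated events under product-related AEs is a separate slip in the same sentence and should be corrected with it.

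**What to change.** Change SAP 12.2 and Protocol 14.5 as follows.

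1. For any AE, product-related AEs, serious AEs and withdrawals due to AE, report the difference in proportions (NORFLO ORO minus placebo) with a two-sided 95% score-type interval (Newcombe or Miettinen-Nurminen).
2. Define product-related as definitely, probably or possibly related, and remove the unrelated category.
3. Keep p-values as descriptive output only, using Fisher's exact test where expected counts are below 5.
4. Add AE rates per patient-year, with a rate ratio only where both arms have events. The denominator must be the time under AE observation that matches the events counted. Treatment duration alone (SAP 12.1) does not match, because Protocol 13.1 also records AEs in periods without product intake.
5. State that a non-significant difference will not be read as evidence of equal safety.

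The cost is SAP and protocol wording and a few lines in Table 14.3.1. AE start and stop dates are already recorded (Protocol 9.1.6), so no new assessments are needed. The downside is that the intervals will be wide, so the safety statement becomes less favourable.
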